## **4. SUBJECT INFORMATION**

The number of subjects in each analysis set will be summarized and listed.

### **4.1. Demographics and Baseline Characteristics**

Demographic and baseline characteristics will be summarized based on treated population and response evaluable population as well.

The demographic characteristics include age (in year, and by category:  $< 65/\geq 65$ ), gender, ethnicity, race, height (cm) and weight (kg).

The baseline disease characteristics include

- Baseline ECOG performance status score
- Baseline PSA level
- Time from initial diagnosis to 1st dose

- 
- Cancer Stage at Diagnosis (I, II, III, IVA, IVB, IVC)
  - Tumor stage at Initial diagnosis (T; N; M)
  - AR positivity (local)
  - AR positivity (central)
  - Staining Pattern (central) (Scatter, Focal, Diffuse)
  - Prior Surgery (yes; no)
  - Prior Radiotherapy (yes; no)
  - Prior lines of systemic therapy (yes; no)
  - Disease status (Locally Advanced, Recurrent/Metastatic)
  - Primary tumor site at Initial Diagnosis (Parotid Gland, Submandibular Gland, Sublingual Gland, Minor Salivary Gland, Other, Could Not Be Specified)
  - Histology Classification (central) (Mucoepidermoid Carcinoma, Adenoid Cystic Carcinoma, Acinic Cell Carcinoma, etc.)

For continuous variables, descriptive statistics (N, mean, standard deviation [SD], median and range [minimum and maximum] and IQ range) will be provided.

For discrete variables, frequency distribution with the number and percentage of subjects in each category will be provided.

#### **4.2. Disposition Information**

Screened subjects and reason for screen failures will be summarized.

The number of subjects in the following disposition categories will be summarized:

- Subjects enrolled
- Subjects in treated population
- Subjects in response evaluable population
- Subjects completing the study
- Subjects who discontinued study treatment
- Reasons for discontinuation of study treatment
- Subjects who discontinued apalutamide
- Reasons for discontinuation of apalutamide
- Subjects who discontinued goserelin
- Reasons for discontinuation of goserelin
- Subjects who terminated study prematurely
- Reasons for termination of study

Listings of subjects will be provided for the following categories:

- Subjects who discontinued study treatment
- Subjects who discontinued apalutamide
- Subjects who discontinued goserelin
- Subjects who terminated study prematurely
- Subjects who were enrolled yet did not receive study treatment.

#### **4.3. Treatment Compliance**

Treatment compliance will be analyzed as part of exposure.

#### **4.4. Extent of Exposure**

The treated population will be used to summarize drug exposure, treatment compliance and dose modifications.

Treatment duration will be defined as the duration from the date of the first dose of study intervention to the date of last dose of study intervention.

#### **Apalutamide**

Subjects should take daily dose based on the protocol during the treatment period unless the subjects experience toxicity that result in protocol-specified dosing modifications. Drug compliance will be summarized and the percent treatment compliance is defined as the number of tablets taken during the study divided by the expected number of tablets, multiplied by 100. The number of tablets taken will be calculated based on the number of tablets actually taken as recorded from subject. A subject's expected number of tablets will be calculated according to the planned treatment regimen. For example, for subjects with no dose modification the expected number of tablets equals the number of assigned tablets per day multiplied by treatment duration, however for subjects with dose reduction the expected number of tablets will be smaller. Subjects with dose modification or skipped dose and the reason for the dose modification will be summarized.

Extent of exposure will be summarized in terms of treatment duration in cycles and in months, which are calculated as the number of days with dosing record divided by 28 (ie, expected number of days in a cycle) and 30.4375 (ie, number of days in a month calculated as  $365.25/12$ ).

#### **Goserelin**

Dose intensity (mg/cycle) and relative dose intensity (%) will be calculated and summarized for goserelin.

The dose intensity will be calculated as cumulative dose divide by the number of treatment cycles.

The relative dose intensity will be calculated as total actual dose divide by total planned dose, multiply by 100.

#### **4.5. Protocol Deviations**

Major protocol deviations and COVID-19 regarding protocol deviations will be summarized using treated analysis set. A corresponding listing for major protocol deviations and COVID-19 regarding protocol deviations is also provided.

#### **4.6. Prior and Concomitant Medications**

Prestudy and concomitant therapies, other than study treatment, taken prior to starting study treatment and those administered during the study will be summarized. Therapies are considered concomitant if taken during the treatment period (within 30 days of the last study intervention dose). Therapies will be summarized by WHO Drug therapeutic class and generic therapy name.

Summaries of concomitant therapies and prestudy therapies will be presented by ATC term.

#### **4.7. Subsequent Anticancer Therapies**

Subsequent therapies received after discontinuation of study treatment will be summarized.

The following imputation rule will be used for missing start dates for subsequent therapies:

- a. If all parts of the start date are missing, the date will be imputed with the date after the discontinuation date.
- b. In the case where only the start day of therapy is missing, it will be replaced by the day after the discontinuation date if the therapy starts in the same month and year as the discontinuation date. Otherwise, it will be replaced by the first of the month.
- c. If both the start day and month of therapy are missing, the start day and month will be replaced by the day and month of the date after the discontinuation date if the therapy and the discontinuation occur in the same year; otherwise, it will be replaced by 1st of January.

### **5. EFFICACY**

This study has 1 primary endpoint, 6 secondary endpoints, and exploratory endpoints. A summary of the planned analyses for efficacy endpoints are listed in [Table 3](#), more details can be found in subsequent sections.

At the interim and final analysis, the primary endpoint (ORR) and the secondary endpoints (CBR, DCR, TTR, DOR) will be analyzed based on the data of the response evaluable participants who are evaluated at least 24 weeks after the initiation of study intervention or confirmed disease evaluation before 24 weeks observation respectively. The other secondary endpoints (OS, PFS) will be analyzed using all available data of treated population. The all available data of response evaluable population at the interim and final analysis will be analyzed as supplemental analysis for primary endpoint and secondary endpoints.

A response of PR or CR must be confirmed by repeat assessments  $\geq 4$  weeks from the initial observation. For a response to qualify as stable disease, follow-up measurements must have met the stable disease criteria at least once at a minimum interval  $\geq 6$  weeks after the first dose of study agent.

In addition, unless specify, disease evaluation is based on the independent radiology review (ICRR).

**Table 3: Summary of the planned analyses for efficacy endpoints**

Endpoint	Analysis Method	
Primary endpoint	Overall response rate (ORR)	Exact test based on binomial distribution Exact Clopper-Pearson 95% CI Waterfall plot Swim lane plot Spider plot
Secondary endpoints	Clinical benefit rate (CBR)	Exact Clopper-Pearson 95% CI
	Disease control rate (DCR)	Exact Clopper-Pearson 95% CI
	Progression-free survival (PFS)	Kaplan-Meier estimates Descriptive summary
	Overall survival (OS)	Kaplan-Meier estimates Descriptive summary
	Time to response (TTR)	Descriptive summary
	Duration of response (DOR)	Kaplan-Meier estimates

Subgroup analyses will be done as exploratory analysis.

## 5.1. Analysis Specifications

### 5.1.1. Level of Significance

The primary endpoint is tested with 1-sided 2.5% level of significance. The testing of the primary endpoint will be performed according to the O'Brien-Fleming boundary based on Lan-DeMets' alpha spending function with a planned Type 1 error of 2.5% (1-sided). The overall Type-1 error is 1-sided 2.5% for analysis of primary endpoint. The futility and efficacy are declared based solely on the independent central radiology review (ICRR) of primary endpoint and [Table 1](#) of [Section 3](#) whose efficacy boundary is calculated based on the O'Brien-Fleming boundary based on Lan-DeMets' alpha spending function. For easy understanding, the two-sided 95% confidence level is used for calculating confidence interval, unless otherwise specified.

### 5.1.2. Data Handling Rules

In general, no imputation method is planned for handling missing or incomplete data unless specified otherwise for a specific endpoint. Sensitivity analyses with censoring rules may be conducted if warranted and will be documented in the clinical study report.

The following imputation rule will be used for missing dates in the assessment of an event:

- a. If the daypart is missing, last day of the month or the last date known alive, whichever is earlier, will be used.
- b. If the day and month parts are both missing, last day of the year (ie, Dec. 31) or the last date known alive, whichever is earlier, will be used.
- c. If the event date is completely missing, then the last date known alive will be used.

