Keys: AR=androgen receptor; β-hCG=beta human chorionic gonadotropin; C1D1=Cycle 1 Day 1; CT=computed tomography; CTC=circulating tumor cell; E2=estradiol; ctDNA/RNA=circulating tumor DNA/RNA; ECG=electrocardiogram; ECOG-PS=Eastern Cooperative Oncology Group performance status; eCRF=electronic case report form; EOT=end-of-treatment; FDG-PET=fluorodeoxyglucose-positron emission tomography; FFPE=formalin-fixed paraffin-embedded; FSH=follicle stimulating hormone; GnRH=gonadotropin-releasing hormone; HER2=human epidermal growth factor receptor 2; HDL=high-density lipoprotein; ICF=informed consent form; LDL=low-density lipoprotein; LH=luteinizing hormone; MRI=magnetic resonance imaging; PK=pharmacokinetic(s); PSA=prostate-specific antigen; q3 cycles=every 3 cycles; ULN=upper limit of normal; T3=triiodothyronine; T4=free thyroxine; TSH=thyroid-stimulating hormone.

Footnotes:

- a. Must sign the ICF before first study-related activity.

- b. Every effort should be made to document radiographic progression, even after discontinuation of treatment for safety or tolerability reasons (eg, AE) but prior to subsequent therapy.
- c. If a participant discontinues study intervention for safety or tolerability reasons (eg, AE), radiographic evaluations must be continued until disease progression but prior to subsequent therapy according to the same schedule as the one of prediscontinuation (every 2 cycles or every 3 cycles beginning at Cycle 13 from Cycle 1 Day 1) unless (s)he withdraws consent for follow-up.
- d. Locally performed. For fasting laboratory assessments, if the participant has not fasted before the visit, the visit may proceed, but the participant must return within 72 hours in a fasted state to provide the necessary sample(s) for the assessments.
- e. Follow-up for survival will continue until death, withdrawal of consent, lost to follow-up or until the end of the study. Deaths regardless of causality will be reported in the eCRF. Serious adverse events that occur after 30 days following the last drug administration thought to be related to study intervention will be collected and reported via the Serious Adverse Event form within 24 hours of discovery or notification of the event and documented (refer to Section 8.3.1).
- f. Fasting state is defined as 8 hours without food or drink, with the exception of water.
- g. A blood sample will be collected at any time between 0.5 to 4 hours after the apalutamide administration.

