4. STUDY DESIGN

4.1. Overall Design

This is an open-label, single-arm, multicenter, Phase 2 study to evaluate the efficacy and safety of apalutamide in combination with a GnRH agonist in participants with AR expressing locally advanced or recurrent/metastatic SGC.

A target of 24 participants will be included in this study and receive apalutamide and a GnRH agonist.

The study will consist of a screening phase, a treatment phase, and a follow-up phase. The study is anticipated to end approximately 42 months after the first participant is consented.

The study will be conducted in an outpatient setting and a treatment cycle is defined as 28 days. Study intervention will continue until disease progression, unacceptable toxicity, death, or the end of the study. Study intervention will be discontinued if a participant meets any of criteria described in Section 7.1, Discontinuation of Study Intervention.

After discontinuing study intervention, participants will be contacted every 6 months (refer to the SoA in Section 1.3) until death or the end of the study.

Participants will be monitored for safety starting from the signing of informed consent until 30 days after the last dose of study intervention. Adverse events including laboratory AEs will be graded and summarized using version 5.0 of the National Cancer Institute-Common Terminology Criteria for AEs (NCI-CTCAE). Dose modifications will be made as required according to dose modification rules (Section 6.6). An independent central radiology review will be used to reduce potential bias during data collection and evaluation of the primary endpoint of ORR and secondary endpoints including PFS (Section 9).

A diagram of the study design is provided in Section 1.2, Schema.

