##### Resolution Date

Partial AE resolution dates not marked as ongoing will be imputed as follows:

- If the resolution date of an adverse event is missing day only, it will be set to the earliest of the last day of the month of occurrence of resolution, the day of withdrawal, study completion, or the day of the date of death, if withdrawal, study completion, or death occurred in that month.

- If the resolution date of an adverse event is missing both day and month, it will be set to the earliest of the date of withdrawal, study completion, December 31 of the year, or the day and month of the date of death, if the death occurred in that year.
- Completely missing resolution dates will not be imputed.

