**Table 5: OS Event and Censoring Method**

Situation	Date of Death or Censoring	Outcome
Death	Date of death	OS event
Other (eg, withdrawal of consent to study participation, lost to follow-up, etc.)	Last known date to be alive	Censored

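### For a partially dated death, the SAP's imputation rule always returns the last date known alive, so the recorded month or year is ignored and OS is dated too early

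*SAP*

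**What the plan says.** SAP section 5.1.2 has one set of rules for incomplete event dates, introduced by "The following imputation rule will be used for missing dates in the assessment of an event".

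- Rule a, day missing: "If the daypart is missing, last day of the month or the last date known alive, whichever is earlier, will be used".
- Rule b, day and month missing: "last day of the year (ie, Dec. 31) or the last date known alive, whichever is earlier, will be used".
- Rule c, date wholly missing: the last date known alive.

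Death is in scope. SAP Tables 4, 5 and 6 label it a PFS, OS and DOR event, and no section exempts it or gives another rule for partial death dates. For a participant not known to have died, Table 5 censors OS at "Last known date to be alive".

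Two other SAP rules for partial dates respect the recorded month. The AE resolution rule in section 2.4, with only the day missing, lets an earlier bound apply only "if withdrawal, study completion, or death occurred in that month". Section 4.7, for a subsequent therapy that starts in a month other than the discontinuation month, says: "Otherwise, it will be replaced by the first of the month".

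On contact frequency, Protocol section 4.1 defines a 28-day cycle and states: "After discontinuing study intervention, participants will be contacted every 6 months". Footnote c of the Schedule of Activities keeps imaging after a stop for toxicity at "every 2 cycles or every 3 cycles beginning at Cycle 13 from Cycle 1 Day 1", that is, every 56 or 84 days.

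**The concern.** Taking the earlier of two dates is a sensible cap for progression, because a participant may be known alive well after the progression month. For a death the cap becomes the whole answer: rules a and b give the same result as rule c. The death is then placed on the date at which a participant not known to have died would be censored. That date can lie before the month or year in which the death is recorded, and so be known to be impossible.

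Every partially dated death shortens OS unless the participant was last known alive on the day of death. PFS and DOR are affected only when death, and not an earlier progression, is the counted event. Partially dated progressions are outside this point; for them the rule can act in the other direction.

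**Working it through.** **Logic.** Let L be the last date known alive, D the true death date, M the last day of the recorded month and Y 31 December of the recorded year. For any death, L ≤ D ≤ M ≤ Y. Hence:

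- rule a: min(M, L) = L
- rule b: min(Y, L) = L

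This held in all 146,365 combinations of a 2022 death date (365 days) with L from 0 to 400 days earlier (401 values). The result equalled the true date only in the 365 cases with L = D, and was never later.

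**Example.** Take L = 10 January 2022 and a death recorded as June 2022. Rule a gives 10 January 2022, which is 142 days before 1 June and 171 days before 30 June. With only the year recorded, rule b gives the same date. By contrast, a progression recorded as June 2022 with L = 1 November 2022 is imputed to 30 June 2022, inside its month.

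**Size of the shift.** The documents do not say how far L lies from D. Assumption: D − L is equally likely to be 1, 2, …, G days, where G is the contact gap. The mean shift is then −(G + 1)/2; for example, −(28 + 1)/2 = −14.5 and −(183 + 1)/2 = −92. The other columns come from enumerating every death date over four years (1,461 days).

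| Gap G (days) | Mean shift, current rule (days) | Dated before recorded month (day missing) | Dated before recorded year (year only) |
|---|---|---|---|
| 28 (treatment cycle) | −14.5 | 47.6% | 4.0% |
| 56 (two cycles) | −28.5 | 73.7% | 7.8% |
| 84 (three cycles) | −42.5 | 82.5% | 11.6% |
| 183 (6-monthly contact) | −92.0 | 92.0% | 25.2% |

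**Effect on the median.** Kaplan-Meier OS medians were simulated with n = 24, exponential survival, follow-up uniform over 24–42 months and each affected death moved back by a uniform 0–6 months (8,000 trials per setting). True medians span the 17 to 44 months cited in Protocol section 2.1. The sample size, survival shape, follow-up and shift are assumptions. Only trials with an estimable median count.

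| True median (months) | Median changes, 1 affected death | Median changes, 2 affected deaths |
|---|---|---|
| 17 | 13.5% | 24.8% |
| 30 | 11.5% | 21.9% |
| 44 | 11.7% | 21.0% |

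When the median moved and stayed estimable, it moved by −1.18 to −1.62 months on average.

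**The case against.** The logic is not disputed. The objections concern how much it matters and what to do.

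- **Rarity.** Protocol section 6.7 has the date of death collected on the eCRF, so partial dates may be few or absent. This stands. The rule exists for the cases that do occur, though, and section 6.7 also allows survival status to be obtained by telephone.
- **Low stakes.** OS, PFS and DOR are descriptive, in a single arm, and the error shortens survival, so it cannot flatter the treatment. This stands and limits the weight of the point. The SAP does not present the rule as deliberately conservative.
- **Small average effect.** The movements of 1.2–1.6 months are conditional on the median moving. Averaged over all trials with an estimable median, one affected death shifts it by 0.14–0.18 months, or about 0.03 months with a 28-day gap. The sampling standard deviation is 4.9–6.5 months, so the bias is about 2–4% of one standard deviation (0.14/6.5 to 0.18/4.9). At a true median of 44 months only about 40% of trials have an estimable median. All of this stands as a description of size.
- **Undefined term.** The SAP does not define the last date known alive. A report of death in June implies survival to 31 May. On that reading a day-missing error is at most about a month and the 92-day figure does not arise. Even then, without a contact in June, the rule returns 31 May, outside the recorded month.
- **Choice of replacement.** First-of-month imputation still leans early. Taking the later of the 15th and the last date known alive has a mean error of about −1 day with 6-monthly contact (range −16 to +14). That is a fair alternative, and either choice respects the recorded month.

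**Conclusion.** The point holds. Followed exactly, SAP 5.1.2 rules a and b give every partially dated death the last date known alive and make no use of the recorded month or year. This needs only that the last date known alive is on or before the death.

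The size rests on a uniform gap between last contact and death: a mean of 14.5 days early with 28-day visits and 92 days early with 6-monthly contact. One affected death would change the OS median in about 12–14% of simulated trials, and two in about 21–25%.

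The overall effect depends on the number of partial death dates, which the documents do not give. ORR, the efficacy and futility boundaries and the Type-1 error are unaffected. The correction should be made because the rule can produce dates known to be impossible and is cheap to repair, but it does not bear on the trial's primary conclusion.

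**What to change.** Add a separate rule for death dates to SAP section 5.1.2:

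- Day missing: use the later of the first day of the recorded month and the day after the last date known alive, capped at the last day of the recorded month.
- Day and month missing: use the later of 1 January of the recorded year and the day after the last date known alive, capped at 31 December of that year.

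Keep current rules a and b for all events other than death, so that no other partial event date is left without a rule. Rule c need not change. The cap matters only when the last contact was on the final day of the recorded period.

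The cost is two SAP sentences and the matching programming, using data already collected. The error is reduced, not removed. Mean error in days under the same uniform-gap assumption:

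| Gap (days) | Current rule | Proposed, day missing | Proposed, year only |
|---|---|---|---|
| 28 | −14.5 | −9.2 | −13.1 |
| 56 | −28.5 | −12.0 | −26.1 |
| 84 | −42.5 | −12.9 | −38.3 |
| 183 | −92.0 | −13.9 | −75.7 |

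With the day missing, the imputed death stays in its recorded month and is at most 30 days early. With only the year recorded, the gain is modest.

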## 5.2. Primary Efficacy Endpoint

As mentioned in the Section 3, the analysis will be conducted based on the data of the fixed number (12 and 24) of response evaluable participants who are evaluated at least 24 weeks after the initiation of study intervention or confirmed disease evaluation before 24 weeks observation.

The same analysis based on all available data of response evaluable population at data cutoff (cutoff date is established by sponsor) is conducted as supplemental analysis.

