## 1.4. Sample Size Justification

In this study, ORR of 40% is assumed (Fushimi 2018). Under the alternative hypothesis for ORR of 40%, using an O'Brien-Fleming boundary based on Lan-DeMets' alpha spending function (Jennison 1999), to achieve at least 80% power for rejecting the null hypothesis for ORR of 14% by exact test based on the binomial distribution while maintaining overall 1-sided Type-1 error below 2.5%, at least 24 evaluable participants will be required. The null hypothesis of ORR of 14% for the threshold value is an estimate based on published data (Viscuse 2019).

An ORR will be tested using exact test based on the binomial distribution, and the null hypothesis for ORR of 14% will be rejected and efficacy will be declared if statistical significance is observed using an O'Brien-Fleming boundary based on Lan-DeMets' alpha spending function as described in Section 3. Futility analysis is also used in this study. Details are described in Section 3. With 24 evaluable participants and 1 interim analysis based on the boundaries, overall Type-1 error will be lower than the one-sided significance level of 2.5% and power will be higher than 80%. The lower limit of 2-sided 95% Clopper-Pearson confidence interval (CI) for ORR will exceed the threshold value of 14% if efficacy is declared based on the boundaries in Table 1.

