## 3. INTERIM AND FINAL ANALYSIS

An interim analysis will be conducted. To control overall Type 1 error, O'Brien-Fleming boundary based on Lan-DeMets' alpha spending function will be used for analysis of primary endpoint based on the independent central radiology review (ICRR), and the null hypothesis for ORR of 14% will be rejected and efficacy will be declared if statistical significance is observed based on the O'Brien-Fleming boundary of Lan-DeMets' alpha spending function. In the interim analysis, futility analysis is also planned, the study will be concluded futile and will be stopped, if the count of responder is 1 or none. The stopping boundaries for efficacy and futility based on the O'Brien-Fleming boundary of Lan-DeMets' alpha spending function are displayed in [Table 1](#). Enrollment will not pause during interim analysis.

In this study, an interim analysis will be performed when 12 response evaluable participants (response evaluable population) who has been evaluated at least 24 weeks from the initiation of study intervention are observed. The interim analysis is performed based on the data from 12 response evaluable participants (response evaluable population) who has been evaluated at least 24 weeks from the initiation of study intervention or whose disease evaluation of primary endpoint has been determined within 24 weeks after the initiation of study intervention. If 13 or more response evaluable participants who meet the condition above are available at the timing of interim analysis, only the data of 12 response evaluable participants who are selected by date of obtaining informed consent will be used for primary analysis at the interim analysis. (If there are multiple response evaluable participants whose date of obtaining informed consent is the same, who are with earlier date of the first study intervention will be used. If informed consent date and first study intervention date are used and response evaluable participant is still not unique, who are with smaller number of study site number will be used. ie, Response evaluable participants are selected in order of the date of obtaining informed consent, the date of first study intervention and study site number from the participants who meet the condition above.) The analysis of primary endpoint using data including 13th or more response evaluable participants (in the same order of above) and thereafter will be used for supplemental analysis.

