**Table 2: Summary of Selected Analyses at the Interim Analysis**

	Analysis	Analysis Set
Subject Information	Summary of Demographics and Baseline Characteristics	Treated, Response evaluable
	Disposition Information	Treated, Response evaluable

	Analysis	Analysis Set
	Summary of Exposure and Dose Adjustment	Treated
	Summary of Prior SGC Related Therapy	Treated, Response evaluable
	Current General Medical History by System Organ Class (SOC) and Preferred Term (PT)	Treated
Efficacy	Summary of Overall Response Rate Including Supplemental Analysis with Expansion Data – ICRR/Investigator Judgement	Response evaluable
	Subgroup Analysis for Overall Response Rate Including Supplemental Analysis with Expansion Data – ICRR Judgement	Response evaluable
	Waterfall Plot and Swimlane Plot Including Supplemental Analysis with Expansion Data – ICRR Judgement	Response evaluable
	Summary of Disease Control Rate Including Supplemental Analysis with Expansion Data – ICRR Judgement	Response evaluable
	Summary of Clinical Benefit Rate Including Supplemental Analysis with Expansion Data – ICRR Judgement	Response evaluable
	Summary of Duration of Response Including Supplemental Analysis with Expansion Data – ICRR Judgement	Responders in Response evaluable
	Summary of Time to Response Including Supplemental Analysis with Expansion Data – ICRR Judgement	Responders in Response evaluable
	Summary of Overall Survival and Kaplan-Meier Plot	Treated
	Summary of Progress-Free Survival and Kaplan-Meier Plot – ICRR Judgement	Treated
Safety	Overall Summary of Treatment-emergent Adverse Events (TEAEs)	Treated
	TEAEs by SOC, PT, and Toxicity Grade	Treated
	Related TEAEs by SOC, PT, Toxicity Grade and Study Agent	Treated
	TEAEs of Special Interest by SOC, PT and Toxicity Grade	Treated
	Serious TEAEs by SOC, PT and Toxicity Grade	Treated
	Related Serious TEAEs by SOC, PT, Toxicity Grade and Study Agent	Treated
	TEAEs leading to Discontinuation of Study Agent by SOC, PT and Toxicity Grade	Treated
	Related TEAEs leading to Discontinuation of Study Agent by SOC, PT and Study Agent	Treated
	TEAEs Leading to Dose Reduction or Interruption of Apalutamide by SOC and PT	Treated
	TEAEs Leading to Dose Interruption or Delay of Goserelin by SOC and PT	Treated
	TEAEs Leading to Death by SOC and PT	Treated
	TEAEs of Toxicity Grade 3 or Greater by SOC and PT	Treated
	Related TEAEs of Toxicity Grade 3 or Greater by SOC, PT and Study Agent	Treated

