### **5.3. Secondary Endpoints**

The analyses of (CBR, DCR, TTR, DOR) will be conducted based on the data of the response evaluable participants who are evaluated at least 24 weeks after the initiation of study intervention or confirmed disease evaluation before 24 weeks observation. The same analysis based on all available data of response evaluable population is conducted as supplemental analysis.

The analyses of (OS, PFS) will be conducted based on treated population using all available data of treated population. Sensitivity analyses will also be performed using the response evaluable population.

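### The supplemental ORR and CBR have no follow-up condition, so participants seen too briefly count as failures and pull both rates down, mainly at the interim

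*SAP*

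**What the plan says.** **The supplemental set in SAP 5, 5.2 and 5.3.** SAP 5 states: "The all available data of response evaluable population at the interim and final analysis will be analyzed as supplemental analysis for primary endpoint", and extends this to the secondary endpoints. SAP 5.2 repeats it for ORR: "The same analysis based on all available data of response evaluable population at data cutoff". SAP 5.3 repeats it for CBR, DCR, TTR and DOR: "The same analysis based on all available data of response evaluable population is conducted as supplemental analysis". None of the three sets a minimum follow-up.

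**Who is response evaluable.** SAP 2.2 asks for local AR positivity, a target lesion confirmed by central review, at least one dose, and one postbaseline disease assessment (or death from progression before it). There is no 24-week condition.

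**The primary set.** SAP 3 and 3.1 admit participants to the fixed 12 or 24 only if they have the Cycle 7 assessment or their outcome was determined earlier: confirmed response, centrally read progression, end of study participation, or subsequent therapy.

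**The supplemental set in SAP 3.** The clause "If 13 or more response evaluable participants who meet the condition above are available at the timing of interim analysis" introduces the choice of the fixed 12. The supplemental analysis is then said to include the 13th and later participants in the same order, and that order is drawn from those who meet the maturity condition. The final analysis is worded in the same way from the 25th participant. Protocol 9.5 orders them by consent date only.

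**Where it is reported.** SAP Table 2 lists "Summary of Overall Response Rate Including Supplemental Analysis with Expansion Data" for the interim, with matching rows for subgroup ORR, CBR and DCR. SAP 3 says enrollment does not pause for the interim.

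**The concern.** A response must be confirmed at least 4 weeks after it is first seen, and CBR through stable disease needs 24 weeks. Someone recently enrolled cannot yet meet either requirement, but a single scan puts that person in the denominator. SAP 5.1.2 plans no general imputation, so the participant counts as a failure because of the calendar, not the treatment.

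At the interim this group is likely to exist: the cutoff is triggered when 12 participants are mature, while others continue to enter. The supplemental ORR and CBR would then look worse than the primary rates for a reason unrelated to efficacy. In a small subgroup a few such participants could move the rate a long way, and subgroups could differ only because their follow-up differs. Two programmers could also build different supplemental sets, one from SAP 3 and one from SAP 5.

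**Working it through.** **1. The plan's own figures.** SAP 1.4 gives "ORR of 40% is assumed", a "null hypothesis for ORR of 14" percent, and "overall 1-sided Type-1 error below 2.5" percent. The boundaries are futility at 1 or fewer and efficacy at 7 or more of 12, then efficacy at 8 or more of 24. The probability of declaring efficacy is

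P(X₁ ≥ 7) + Σ over x = 2 to 6 of P(X₁ = x) · P(X₂ ≥ 8 − x), with X₁ and X₂ each binomial on 12.

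- At 14%: 0.0133, against 1.3% in Protocol 9.5.
- At 40%: 0.8054, against 80.5% in Protocol 9.5.

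Both reproduce. They involve only the fixed 12 and 24, so the supplemental set cannot change them.

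**2. What a short follow-up allows.** Imaging is at Cycles 3, 5 and 7 (Protocol 1.3), with 28-day cycles: day 56, 112 and 168 after first dose, or weeks 8, 16 and 24.

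- *ORR:* one scan cannot be a confirmed response, and the next scheduled scan is at week 16. A response first seen at week 16 is normally still unconfirmed before week 24.
- *CBR:* before week 24 nobody can have stable disease for 24 weeks.
- *DCR:* stable disease needs one qualifying assessment at least 6 weeks after first dose. The first scan is at week 8, or week 7 with the 7-day imaging window, so it qualifies.

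**3. Size by formula.** Let N be mature participants with true rate p, and m be single-scan, non-progressed participants who cannot yet count. The expected rate is p · N / (N + m). The documents do not give m, and the true CBR of 60% is also an assumption.

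| Analysis | m | ORR (p = 40%) | CBR (p = 60%) |
|---|---|---|---|
| Interim, N = 12 | 2 | 34.3% | 51.4% |
| Interim, N = 12 | 4 | 0.40 × 12/16 = 30.0% | 0.60 × 12/16 = 45.0% |
| Interim, N = 12 | 8 | 24.0% | 36.0% |
| Final, N = 24 | 1 | 38.4% | 57.6% |
| Final, N = 24 | 2 | 36.9% | 55.4% |
| Final, N = 24 | 4 | 34.3% | 51.4% |

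**4. DCR.** Take an assumed true DCR of 80%, N = 12 and m = 4. If the added single-scan participants include progressed and non-progressed in the usual mix, (9.6 + 3.2)/16 = 80%. If only non-progressed ones are added, (9.6 + 4)/16 = 85%. Neither is a downward bias.

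**5. Size by simulation at the interim.** Assumptions: true ORR 40% and CBR 60%; responses first seen at week 8, 16 or 24 in 70%, 20% and 10%; confirmation 8 weeks later; cutoff when the 12th participant reaches week 24; random accrual capped at 24; everyone evaluable after the week-8 scan; 20,000 runs per rate.

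| Accrual per month | Under 24 weeks / in set | Supplemental ORR | ORR, first 12 | Supplemental CBR |
|---|---|---|---|---|
| 1 | 3.8 / 15.7 | 33.5% | 38.9% | 49.5% |
| 2 | 7.5 / 19.3 | 29.5% | 38.2% | 43.0% |

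From 0.75 to 3 participants per month the supplemental ORR runs from 34.7% to 27.6%, against 39.3% to 37.7% in the first 12. The first 12 fall slightly below 40% because a response first seen at week 24 may still await confirmation at the cutoff.

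**The case against.** **No decision depends on it.** SAP 3 and 5.1.1 tie efficacy and futility to the fixed-number, centrally reviewed primary analysis. The SAP's amendment history adds that interim results were not meant for the New Drug Application. This stands, and it limits the point to the supplemental tables. A reader might infer that Type I error, power or the stopping rule is compromised; they are not.

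**Reporting all available data is a legitimate description.** SAP 5.2.1 plans response listings, a spider plot and swim lane plots, so short follow-up is visible, and no passage says the supplemental analysis exists to check the fixed 12 or 24. This is fair. But the rate itself would still mix efficacy with follow-up time, and no count of undetermined participants is planned beside it.

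**The affected number can be overstated.** The 3.8 and 7.5 above include confirmed responders and early progressors, whose outcomes SAP 3.1 treats as determined. If two-thirds of non-responders progress, evenly at weeks 8, 16 and 24 (an assumption), about 2.5 and 4.9 remain undetermined. This stands for the counts. The fall in ORR does not depend on how those participants are labelled.

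**SAP 3 is not flatly contradicted.** A reader might infer a contradiction, but SAP 3 implies maturity only through its ordering rule and never states an exclusion. Protocol 9.5 does not attach the condition to its supplemental sentence. The wording is unreconciled, no more.

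**Conclusion.** The point holds for the supplemental ORR, including the subgroup ORR, and for the supplemental CBR. As written, the SAP places non-progressed participants with too little follow-up in the denominator, where they can only lower the rate. The direction follows from the scan schedule, the confirmation rule and the 24-week requirement. The size rests on accrual and response timing, which the documents do not give: 4 single-scan, non-progressed participants added to 12 mature ones take an expected ORR of 40% to 30%, and an assumed CBR of 60% to 45%.

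The effect belongs mainly to the interim. At the final analysis it is limited to participants beyond the 24th, with a target of about 24. It arises only if such participants are present at the cutoff.

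Because DCR shares the same supplemental set, a reader might infer that it is biased downward too. The documents do not support that, since one week-8 scan without progression already counts as disease control.

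**What to change.** In SAP 5, 5.2 and 5.3, restrict the supplemental ORR (with its subgroups) and CBR to response evaluable participants whose first dose was at least 24 weeks before the cutoff, using all their data to the cutoff. This applies one follow-up rule whatever the outcome.

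State the same rule in SAP 3, and note there that it differs from the SAP 3.1 condition for the fixed 12 and 24, which also admits outcomes determined before 24 weeks. Carrying SAP 3.1 over unchanged would admit recent participants with early progression or early confirmed response and leave out those still stable.

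Report the number of participants under 24 weeks beside the supplemental tables, and keep them in the listings, swim lane plots and spider plot.

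The cost is SAP wording and slightly fewer participants in the supplemental interim tables.
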